## PROTOCOL VERSION HISTORY

**Section 5.2 Exclusion Criteria:** Removed “exclusion criteria” of (1) recurrent/new primary cancer following trial registration and (2) major surgery following trial registration. These criteria were incorrectly listed as exclusion criteria even though their determination occurred after a patient was enrolled (and thus they cannot, by definition, be exclusion criteria).

**Section 5.5 Strategies for Recruitment and Retention:** Changed target accrual from 48 to 52 patients to reflect a higher than anticipated rate of patients discontinuing the study due to recurrent or second primary cancers (**Section 7.2**). The evaluable sample size remains unchanged (N=44).

**Section 7.2 Participant Discontinuation/Withdrawal from the Study:** Refined criteria for study discontinuation to clarify the difference between an exclusion criterion (which is determined at the time of study accrual) and criteria for study discontinuation (which are determined after a patient accrues to the study). The criteria (recurrence or second primary cancer; major head and neck surgery) and rationale (these events/.medical conditions are such that continued f/u of the patient in the study is not in the participant’s best interest and would confound interpretation of the study) remain the same but are now appropriately described as criteria for discontinuation instead of exclusion criteria.

**Section 9.2 Sample Size Determination:** Changed target accrual from 48 to 52 patients to reflect a higher than anticipated rate of patients discontinuing the study due to recurrent or second primary cancers (**Section 7.2**). The evaluable sample size remains unchanged (N=44).

**Section 9.3 Population for Analyses:** Amended to reflect updates to eligible vs evaluable population as described in **Sections 5.2 and 7.2**

**Section 10.4 Protocol Amendment History:** Updated to reflect protocol revisions noted herein.

## STATEMENT OF COMPLIANCE

The trial will be conducted in accordance with International Council on Harmonisation Good Clinical Practice (ICH GCP), applicable United States (US) Code of Federal Regulations (CFR), and the National Cancer Institute (NCI) Terms and Conditions of Award. The Principal Investigator (PI) will assure that no deviation from, or changes to the protocol will take place without prior agreement from the funding agency and documented approval from the Institutional Review Board (IRB), and the Investigational New Drug (IND) or Investigational Device Exemption (IDE) sponsor, if applicable, except where necessary to eliminate an immediate hazard(s) to the trial participants. All personnel involved in the conduct of this study have completed Human Subjects Protection and ICH GCP Training.

[figure not shown]
The protocol, informed consent form(s), recruitment materials, and all participant materials will be submitted to the IRB for review and approval. Approval of both the protocol and the consent form(s) must be obtained before any participant is consented. Any amendment to the protocol will require review and approval by the IRB before the changes are implemented to the study. All changes to the consent form(s) will be IRB approved; a determination will be made regarding whether a new consent needs to be obtained from participants who provided consent, using a previously approved consent form.

## 1 PROTOCOL SUMMARY

### 1.1 SYNOPSIS

Title:	A Single-Site, Parallel-Group, Randomized-Controlled Pilot Trial Comparing BRIGHT with Active Control in Reducing Body Image Disturbance Among Head and Neck Cancer Survivors (BRIGHT 2.0)
Grant Number:	R21CA245941
Study Description:	In this pilot randomized controlled trial, we will evaluate the preliminary clinical impact and underlying behavioral mechanism of BRIGHT (Building a Renewed ImaGe after Head & neck cancer Treatment), a novel 5-session, manualized cognitive behavioral therapy (CBT) intervention to treat body image disturbance (BID) in head and neck cancer (HNC) survivors. We hypothesize that BRIGHT will decrease BID relative to active control (AC; patient-centered videos about HNC survivorship care) through improvements in body image coping behavior.
Objectives:	
Primary Objective: To assess the clinical efficacy of BRIGHT compared with AC on BID in HNC survivors as determined by change in Body Image Scale (BIS) scores at 1-month post-intervention relative to baseline.
 
Select Secondary Objectives:
 

1. To assess the clinical efficacy of BRIGHT compared with AC on BID in HNC survivors as determined by change in IMAGE-HN scores at 1-month post-intervention relative to baseline

2. To explore the behavioral mechanism of action of BRIGHT on changes in BID in HNC survivors as measured by the change in Body Image Coping Strategies Inventory (BICSI) scores at 1-week post-intervention relative to baseline.

3. To provide preliminary estimates of the clinical effect of AC on BID in HNC survivors as determined by change in BIS scores at 1-month post-intervention.

4. To estimate the activity of BRIGHT compared with AC on BID in HNC survivors in terms of clinical response as measured by improvement in BIS scores at 1-month post-intervention relative to baseline.

5. To assess the clinical efficacy of BRIGHT compared with AC on BID in HNC survivors as determined by change in BIS scores at 3-months post-intervention relative to baseline.

6. To evaluate the preliminary clinical efficacy of BRIGHT compared with AC on changes in psychological, emotional, and social well-being in HNC survivors at post-treatment and 1- and 3-months post-intervention relative to baseline
7. To evaluate the feasibility of BRIGHT, delivered via a tablet-based telemedicine, as a strategy to treat BID in HNC survivors
8. To evaluate the acceptability of BRIGHT to as a strategy to treat BID in HNC survivors
9. To determine the association of demographic variables with therapeutic alliance between the study participant and psychologist

**Endpoints:**

Primary Endpoint:

Change in BIS score from baseline to 1-month post-intervention

Select Secondary Endpoints:

1. Change in IMAGE-HN score from baseline to 1-month post-intervention.
2. Change in BICSI scores from baseline to 1-week post-intervention
3. Clinical response (BIS score at 1-month post-intervention that is less than the BIS score at baseline)
4. Change in BIS score from baseline to 3-months post-intervention
5. Change in Shame and Stigma Scores from baseline to 1- and 3-months post-intervention
6. Change in PROMIS SF v1.0-Depression 8a scores from baseline to 1-month post-intervention and baseline to 3-months post-intervention
7. Change in PROMIS SF v1.0-Anxiety 8a scores from baseline to 1-month post-intervention and baseline to 3-months post-intervention.
8. Change in PROMIS SF v2.0-Social Isolation 8a scores from baseline to 1-month post-intervention and baseline to 3-months post-intervention
9. Change in PROMIS SF v2.0-Satisfaction with Social Roles and Activities 8a scores from baseline to 1-month post-intervention and baseline to 3-months post-intervention

**Study Population:**

The study population will consist of head and neck cancer survivors with no evidence of disease, 18 years of age or older, of all races and sexes, with BID following treatment of HNC

**Phase or Stage:**

[figure not shown]
N/A

**Description of  
Sites/Facilities Enrolling  
Participants:**

The study will be conducted, and participants enrolled, at a single site, the Medical University of South Carolina (MUSC) Hollings Cancer Center (HCC) Head and Neck Tumor Center. The Head and Neck Tumor Center is a high-volume, multidisciplinary center designed for unsurpassed clinical care and optimized for integration of research activities. The Head and Neck Tumor Center is a regional center of excellence for HNSCC clinical care.

Description of Study	BRIGHT is 5 sessions of weekly, 60-minute, tablet-based, manualized
Intervention/Experimental Manipulation:	individual tele-CBT targeting the behavioral and attitudinal components of HNC-related BID.
Study Duration:	24 months
Participant Duration:	4 months

## 1.2 SCHEMA

**Fig. 1. Study Schema.** Following completion of baseline questionnaires, participants will be randomized to 5 weeks of BRIGHT or AC, then complete validated measures of BID, body image coping behavior and psychological, social, and emotional well-being at 1-week, 1-month, and 3-months post-intervention to assess the impact of BRIGHT on changes in BID and the role of body image coping behavior as a mediator of changes in BID.

### 1.3 SCHEDULE OF ACTIVITIES

	Pre Screen (-60 to 1)	Visit 1 Day 1 a	Visit 2 Day 8 ±14	Visit 3 Day 15 ±7	Visit 4 Day 22 ±7	Visit 5 Day 29 ±7	Visit 6 Day 36 ±7	Visit 7 Day 43 ±14	Visit 8 Day 64 ±14	Visit 9 Day 124±14	For Details, see section
Informed Consent											
Review Study Eligibility b	X										5
Informed Consent c	X										10.1.1
Study Procedures											
Randomization		X									6.3
Demographics		X									8.1
Clinical and Oncologic History		X									8.1
ASI-R		X									8.1
Monitoring											
AS/SAE Assessment			X	X	X	X	X	X	X	X	8.3
Medication Assessment			X	X	X	X	X	X	X	X	8.3
Intervention Administration											
BRIGHT or AC			X	X	X	X	X				6.1
Efficacy Evaluation											
Body Image Scale d	X							X	X	X	8.1
IMAGE-HN d		X						X	X	X	8.1
PROM Assessments											
BICSI d		X						X	X	X	8.1
Shame and Stigma Scale d		X							X	X	8.1
PROMIS SF v1.0- Depression 8a d		X							X	X	8.1
PROMIS SF v1.0- Anxiety 8a d		X							X	X	8.1
PROMIS SF v2.0- Social Isolation 8a d		X							X	X	8.1
PROMIS SF v2.0- Social Roles 8a d		X							X	X	8.1
EORTC QLQ-HN35 d		X							X	X	8.1
Other Evaluations											

Intervention Fidelity		X	X	X	X	X					6.2
Patient Adherence			X	X	X	X					6.4
Program Evaluation								X			8.1
WAI-SR				X			X				8.1

a: Every effort should be made to minimize the time between randomization and starting treatment
 
b: Eligibility assessed using information in the electronic medical record as well as a screening Body Image Scale
 
c: Written informed consent and HIPAA must be obtained prior to performing and protocol-specific procedures, including baseline evaluations. To optimize participant and researcher safety during the COVID-19 pandemic, informed consent may be obtained in person using a paper informed consent document or electronically using the eConsent.
 
d: Sites are encouraged to administer PROMs using a site-based electronic device. If that is not feasible, administration of PROMs using a paper-based format is also acceptable. Sites are encouraged to align PROM assessments with clinic visits to facilitate in-person collection. In situations in which in-person collection is not feasible, PROMs may be collected via mail or email at the study coordinator's discretion. When possible, PROMs should be completed prior to any other study procedures (following informed consent) and before clinic visits in which clinical information will be discussed to avoid biasing the patient's responses to the questions.
											

Acronyms: AC, Active Control; AE, Adverse Event; ASI-R, Appearance Schemas Inventory-Revised; BICSI, Body Image Coping Strategies Inventory; BRIGHT, Building a Renewed ImaGe after Head & neck cancer Treatment; IMAGE-HN; Inventory to Measure and Asses imaGe disturbancE-Head & Neck; SAE, Serious Adverse Event; WAI-SR, Working Alliance Inventory-Short Revised
											

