In this proposal, we extend our initial research with a pilot randomized controlled trial (RCT) to examine the clinical impact and behavioral mechanistic underpinnings of BRIGHT on BID in HNC survivors. This proposed project will evaluate the preliminary clinical impact and behavioral mechanism of a novel psychobehavioral intervention delivered via a scalable, tablet-based telemedicine platform, thereby advancing our conceptual understanding of BID and establishing new treatment paradigms to directly address the lack of effective treatment for BID in HNC survivor. HNC survivors with BID will be randomized to 5-weeks of tablet-based BRIGHT or tablet-based active control (AC) (patient-centered videos about HNC survivorship care. Participants will complete the Body Image Scale (a validated measure of BID; primary endpoint), the Body Image Coping Strategies Inventory (a validated measure of body image coping behavior; behavioral mediator) and measures of psychological, social, and emotional well-being (secondary endpoints) at baseline, 1-week, and 1-month and 3-month post-intervention.

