**Table 3. Study Objectives and Endpoints**

OBJECTIVES	ENDPOINTS
To provide preliminary estimates of the clinical effect of AC on BID in HNC survivors as determined by change in BIS scores at 1-month post-intervention relative to baseline	Change in BIS score from baseline to 1-month post-intervention
To estimate the activity of BRIGHT compared with AC on BID in HNC survivors in terms of clinical response as measured by improvement in BIS scores at 1-month post-intervention relative to baseline	Clinical response (BIS score at 1-month post-intervention that is less than the BIS score at baseline)
To assess the clinical efficacy of BRIGHT compared with AC on BID in HNC survivors as determined by change in BIS scores at 3-months post-intervention relative to baseline	Change in BIS score from baseline to 3-months post-intervention
To evaluate the preliminary clinical efficacy of BRIGHT compared with AC on changes in psychological, emotional, and social well-being in HNC survivors as determined by change in respective PROM scores at 1- and 3-months post-intervention relative to baseline	Change in Shame and Stigma Scores from baseline to 1- and 3-months post-intervention Change in PROMIS SF v1.0-Depression 8a scores from baseline to 1-month post-intervention and baseline to 3-months post-intervention Change in PROMIS SF v1.0-Anxiety 8a scores from baseline to 1-month post-intervention and baseline to 3-months post-intervention. Change in PROMIS SF v2.0-Social Isolation 8a scores from baseline to 1-month post-intervention and baseline to 3-months post-intervention Change in PROMIS SF v2.0-Satisfaction with Social Roles and Activities 8a scores from baseline to 1-month post-intervention and baseline to 3-months post-intervention Change in EORTC QLQ-HN35 scores from baseline to 1-month post-intervention and baseline to 3-months post intervention
Feasibility	
To evaluate the feasibility of BRIGHT, delivered via a tablet-based telemedicine, as a strategy to treat BID in HNC survivors	Intervention session duration (minutes) Intervention session completion rate Number of technical issues with tablet platform Return of study-issued tablet Study dropout
Acceptability	
To evaluate the acceptability of BRIGHT to as a strategy to treat BID in HNC survivors	Timing of Intervention (0-5 Likert scale) Method of Intervention delivery (0-5 Likert scale) # of Intervention sessions (0-5 Likert scale)

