### 5.5.3 PLANNED SCREENING AND RECRUITMENT STRATEGIES

We will screen for potential participants using the electronic medical record (EMR) for the Head and Neck Tumor Center clinical schedule in collaboration with the HNC clinical team. To screen for study eligibility, the research staff will use the EMR to review clinic schedules for new or returning patients with an appointment who are potentially eligible for the study. These appointments will include both in-person clinic visits to the MUSC Head and Neck Tumor Center or a telemedicine visit with a head and neck oncology provider. Clinic rosters will be reviewed at a minimum of once per week, or more frequently if indicated by changes to the clinic schedule. As such, screening will generally be performed within 7 days of enrollment. After a patient who is potentially eligible for the study is identified, the patient will be contacted during the previously identified in-person clinic visit within the MUSC Head and Neck Tumor Center or the telemedicine visit with the head and neck oncology provider to discuss participation in the trial. If it becomes clear that further information is needed to determine study eligibility, the patient will be re-screened pending evaluation of the additional information.

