## 8 STUDY ASSESSMENTS AND PROCEDURES

### 8.1 ENDPOINT AND OTHER NON-SAFETY ASSESSMENTS

To screen for study eligibility, the research staff will use the EMR to review clinic schedules for new or returning patients with a physical appointment in the MUSC Head and Neck Tumor Center or telemedicine visit with a head and neck oncology provider who are potentially eligible for the study. Clinic rosters will be reviewed at a minimum of once per week, or more frequently if indicated by changes to the clinic schedule. As such, screening will generally be performed within 7 days of enrollment. After a patient who is potentially eligible for the study is identified, the patient will be contacted at the previously identified clinic visit (either physically within the MUSC Head and Neck Tumor Center or during the telemedicine visit) to discuss participation in the study as described below. The study coordinator who is screening the clinic schedule weekly will determine whether or not the potential trial participant has consented in EPIC to participate in research studies. For patients who have consented in EPIC to participate in research studies, the study coordinator will recruit using existing protocols for face-face clinic-based recruitment and study-specific documents to describe the study. For patients who have not consented in EPIC to participate in research studies, the head and neck oncology provider for the patient will notify the patient of the study and introduce the study to the potential participant. Following this introduction, if the potential participant is interested in learning additional information about the trial, the study coordinator will recruit using existing standard operating procedures for clinic-based or telemedicine-based recruitment. Patients who meet demographic and oncologic inclusion criteria will complete a screening BIS questionnaire; those with scores  $\geq 10$  will be eligible for the study. Those with scores  $< 10$  will not be eligible for the study, their BIS questionnaire will be shredded, and no personal information about the patient will be saved.

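### As scheduled, the BIS score that decides eligibility (10 or more) is also the baseline for BIS change, so regression to the mean enters the within-AC change and the response proportions, though not the randomised primary contrast.

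*Combined protocol and SAP*

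**What the plan says.** Section 1.3 (Schedule of Activities) is the only place that times the BIS. It marks the scale in the column headed "Pre Screen (-60 to 1" and then at Visits 7, 8 and 9. Visit 1 has no BIS, although IMAGE-HN, BICSI, the Shame and Stigma Scale, the PROMIS forms and the QLQ-HN35 all have their baseline there.

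The pre-screen score is the selection score. Footnote b to the schedule reads "Eligibility assessed using information in the electronic medical record as well as a screening Body Image Scale". Section 5.1 requires a BIS of at least 10. Section 8.1 says "Patients who meet demographic and oncologic inclusion criteria will complete a screening BIS questionnaire" and admits those scoring 10 or more.

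Section 2.1 lists the BIS among measures completed "at baseline, 1-week, and 1-month and 3-month post-intervention", with no visit attached. Sections 1.2, 4.1 and 9.2 also refer to baseline questionnaires or assessments without dating a second pre-treatment BIS. On timing, Section 5.5.3 states that "screening will generally be performed within 7 days of enrollment", and Section 8.1 agrees.

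Two outputs depend on change from this baseline within an arm. Table 3 has the objective "To provide preliminary estimates of the clinical effect of AC on BID in HNC survivors", read from the AC arm's own BIS change at 1 month. Section 8.1 defines response as any 1-month BIS below the baseline BIS. The primary model in Section 9.4.2 takes change from baseline as its response and lists no baseline BIS covariate.

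**The concern.** Patients who pass a cut-off on a score with measurement error include some whose score was high by chance on that day. If that score is also the baseline, the next measurement is lower on average even when nothing has changed. A fresh score at Visit 1 would not carry that selection error.

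The outputs exposed are the ones this pilot is meant to hand on. Section 4.2 justifies the randomised design partly by the wish to measure the control group precisely, and Section 9.2 says the results will guide and power a larger trial. A within-AC fall that is partly an artefact would be read as an effect of the control. Because response needs a fall of only one point, a small shift reclassifies patients in both arms.

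**Working it through.** **Figures in the plan.** The documents give no figure for regression to the mean. The planning values used here come from Section 9.2: control change 0.2 with SD 5.9, 22 patients per arm, and 80.2% power for a standardised effect of 0.78 at two-sided alpha 0.1. A two-sample t-test calculation gives 81.6%, close to the stated power.

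**Assumed inputs.** The mean, SD and retest correlation r of the BIS in screened patients are not given. I assume SD 6 and r from 0.7 to 0.9, and let the mean follow from the share of patients who pass the threshold.

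**Fall from selection alone.** For a normal score cut at 9.5 (the lower edge of an integer score of 10) and z = (9.5 − mean)/6:

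fall = (1 − r) × 6 × φ(z) / (1 − Φ(z))

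| Share passing | Mean | z | 6φ(z)/(1 − Φ(z)) | Fall, r = 0.9 | Fall, r = 0.7 |
|---|---|---|---|---|---|
| 91% | 17.5 | −1.34 | 1.07 | 0.11 | 0.32 |
| 66% | 12 | −0.42 | 3.32 | 0.33 | 1.00 |
| 53% | 10 | −0.08 | 4.47 | 0.45 | 1.34 |
| 40% | 8 | 0.25 | 5.78 | 0.58 | 1.73 |

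The 91% is the share of pilot accruals who would have met the new threshold (Section 5.5.2). A simulation with scores rounded and held to 0–30 agrees with the formula: 1.74 for mean 8, r 0.7, and 0.34 for mean 12, r 0.9.

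**AC response.** With planned change 0.2, SD 5.9 and a half-point continuity correction:

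P(response) = 1 − Φ((0.5 − 0.2 − fall)/5.9)

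- No fall: 1 − Φ(0.051) = 48.0%.
- 91% passing: 48.7% at a fall of 0.11 and 50.1% at 0.32.
- 40–66% passing: 50.0% at 0.3 and 59.4% at 1.7.

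**Consistency of the two steps.** SD 6 with r of 0.7 to 0.9 implies a change SD of 6 × √(2(1 − r)), which is 4.6 to 2.7 and not 5.9. A change SD of 5.9 would imply r = 1 − 5.9²/72 = 0.52. At that correlation the falls would be larger: 0.52 if 91% pass and 1.6 to 2.8 if 66% to 40% pass. The response figures are therefore indicative only.

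**Effect of a Visit 1 baseline.** I simulated a stable trait plus independent noise, with mean 8, SD 6, r 0.7 and no treatment effect. Moving the baseline from the screening score to a separate score cuts the AC fall from 1.74 to 0.01 and response from 61% to 46%. With mean 10 and r 0.8, the fall goes from 0.91 to 0.00 and response from 54% to 45%. If the correlation decays with time, some regression remains.

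**Between-arm response.** With a true effect of 4.4 points in the first case, response is about 90% against 61% from the screening baseline (29 points apart) and 80% against 46% from a separate one (34 points apart). The size of the response difference can therefore move, although both arms are affected alike.

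**The case against.** **The schedule may simply omit a Visit 1 BIS.** Section 2.1 lists the BIS at baseline, and no passage says that the screening score is the baseline. If a Visit 1 BIS is in fact collected and used, most of the effect goes. This stands as a reason to reconcile the passages; the schedule would then need correcting.

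**Selection may be mild.** The only figure in the documents on how hard the threshold selects is the 91%, which gives a fall of 0.1 to 0.3. This is a fair limit on the lower scenario, but it appears to be 10 of 11 patients (exact 95% interval 59% to 99.8%), and it describes those who accrued, not all who were screened.

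**The AC estimate is imprecise anyway.** With 22 patients and SD 5.9, its standard error is 5.9/√22 = 1.26 and its 95% half-width is 2.6, more than any fall in the table. It also contains natural history whichever baseline is used. Both are true, but imprecision does not remove a bias that has a known direction and a cheap remedy.

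Four stronger readings are tempting, and the documents do not support them.

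- A reader might infer that the primary comparison is biased. Selection precedes randomisation and acts equally on both arms in expectation, so it is not.
- A reader might infer that planned power is overstated because the pilot's 4.6 contains regression and the cohort's 0.2 does not. The documents give no BIS threshold for the cohort, and the pilot admitted scores above 1, so this cannot be established.
- A reader might take baselines to be typically 60 days old. Sixty days is the window limit; screening is generally within 7 days of enrolment. The loss of precision and the date mismatch with BICSI in the exploratory mediation analysis are usually small.
- A reader might infer that the primary baseline is taken before consent. Footnote c says consent "must be obtained prior to performing and protocol-specific procedures, including baseline evaluations", and the schedule puts consent in the same pre-screen column. The rule in Section 8.1 on destroying forms that score below 10 leaves the order unclear, but does not show a breach.

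**Conclusion.** The point holds as a design weakness that should be fixed, not as a threat to the primary test. Followed as scheduled, the selection score is the BIS baseline. That adds an artefactual fall to the within-AC change and raises the response proportions in both arms.

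Assuming SD 6 and retest correlation 0.7 to 0.9, the fall is about 0.1 to 0.3 points if 91% pass the threshold and 0.3 to 1.7 if 40% to 66% pass, compared with a planned control change of 0.2. With the planned SD of 5.9, AC response moves from 48% to about 49–50% or 50–59% respectively. The direction follows from the design. The size rests on assumed values and cannot be settled from the documents.

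**What to change.** Add the 10-item BIS to Visit 1, after consent and before randomisation, with the other questionnaires. Define it as the baseline for every BIS change and for response, and keep the screening BIS for eligibility only. Bring Sections 1.3, 2.1 and 8.1 into agreement on this, and state when the screening BIS is taken relative to consent.

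For patients already enrolled without a Visit 1 BIS, use the screening score and flag it. Add a sensitivity analysis that uses the screening BIS as baseline for all patients, so that one definition covers everyone. State that the within-AC change and the single-arm response rates are not read as treatment effects. Adjusting the primary model for baseline BIS could help the contrast, but would not remove regression from the within-AC estimate.

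The cost is ten more items at an existing visit, a short amendment, and a mixed source of baseline for patients enrolled before it. Accrual has begun, since Section 9.2 cites interim accrual data, so that last cost is real in a trial of 44 evaluable patients; the sensitivity analysis is there to address it.
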